3.1.1. Description of target group

The aim of both studies is to detect early risk for problematic internet use and prevent the development of addictive usage patterns across the whole well-being spectrum, rather than to treat an already developed pathological use. The whole adolescent population is therefore included rather than specific subgroups. The study population will consist of young adolescents of all genders between 12 and 16 years, recruited from schools with different socioeconomic backgrounds and from rural and urban areas. We strive to include young people from low/middle income families who might be especially vulnerable for PUI. The BootStRaP study is designed to evaluate and moderate online behaviour among young people using mobile devices. Therefore, it is a necessary condition, that young people involved have routine and exclusive access to a mobile device to be able to take part in the study.

The eligibility criteria are:

- Age between 12 and 16 years
- Routine access to a mobile device
- Student at a school involved in the study

The exclusion criteria are:

- No exclusive access to a mobile phone
- Phone operating systems older than 15.6 for iOS or 10 for Android

3.2. Interventions

The two digital interventions developed and refined during the pilot study will be implemented in both the pilot and the RCT. These interventions are underpinned by behavioural change theory, specifically the Behaviour Change Wheel (BCW) (Michie et al., 2011), the COM-B model (Capability, Motivation, Opportunity and Behaviour), and PRIME (Plans, Evaluations, Motives, Impulses and Responses) Theory of Motivation (West & Michie, 2020). Designed to reduce PUI in adolescents, the interventions integrate evidence-based techniques to support emotional regulation and inhibitory control through interactive, personalised, and engaging digital content.

Alignment with Behaviour Change Frameworks

Behaviour Change Wheel (BCW):

- Education: Modules provide knowledge about PUI, emotional regulation, and impulsivity.
- Persuasion: Personalised feedback and motivational prompts encourage reflection and change.
- Enablement: Exercises and challenges build confidence and reduce psychological barriers.
- Training: Participants practise emotion regulation and inhibitory control strategies.
- Modelling: Examples and scenarios demonstrate adaptive behaviours.

COM-B Model:

- Capability: Built through educational content and skill development.
- Opportunity: Created via structured digital environments and real-life application prompts.
- Motivation: Enhanced through emotionally engaging content, feedback, and goal setting.

PRIME Theory:

- Plans: Participants are guided to set intentions and behavioural goals.
- Responses: Interactive tasks prompt immediate engagement with new behaviours.
- Impulses and Motives: Addressed through content targeting emotional and cognitive drivers of PUI.

Emotional (Affect) Regulation Intervention

This intervention aims to enhance emotional awareness and promote emotional competence in adolescents at risk of PUI. It begins with motivational modules on PUI, encouraging reflection through self-assessment, personalised feedback, and exercises to build confidence and readiness for change. The second phase focuses on developing functional emotion regulation skills using interactive, reflective, and gamified exercises.

Grounded in the BCW (Michie et al., 2011), COM-B model, and PRIME Theory (West & Michie, 2020), the intervention incorporates several mechanisms:

- **Education:** Informative content on emotions and PUI enhances understanding and capability. Educational games have been shown to reduce negative emotional experiences (Ferrari et al., 2022; Reynard et al., 2022).
- **Persuasion:** Personalised feedback and emotionally engaging messages promote motivation and behavioural reflection (Heijde et al., 2015; Yan et al., 2020).

- **Reframing:** Cognitive restructuring and self-monitoring support behavioural change, as shown in CBT-based interventions (Du et al., 2010; Park, S et al., 2016).
- **Enablement:** Confidence-building exercises, such as emotion memory games, reduce psychological barriers and support skill development (David et al., 2024).
- **Gamification:** Therapeutic games encourage the application of emotion regulation strategies in daily life, improving outcomes in PUI and emotional control (Ayub et al., 2023; David et al., 2024).
- **Behavioural Activation:** Participants are encouraged to try alternative, positive behaviours (e.g. reading, social interaction), which reduce maladaptive patterns (Park, S et al., 2016).

The intervention is tailored: those at higher risk receive in-depth modules on emotional regulation, expectations, and the link to PUI, while lower-risk participants receive general guidance on internet use and emotion regulation. The programme aims to foster adaptive emotional functioning and reduce risk behaviours (David & Fodor, 2023; Houck et al., 2022; Smith et al., 2024).

For a detailed week-by-week breakdown and more information on each component of the intervention in relation to behaviour change see Appendix A.

Inhibitory (Executive) control Intervention

This intervention aims to help adolescents understand and manage impulsivity and compulsive behaviours linked PUI. It begins with motivational modules encouraging reflection on internet use, supported by self-assessments, personalised feedback, and confidence-building exercises. The second phase focuses on strengthening inhibitory control through interactive challenges, educational content, and practical strategies.

The intervention is grounded in the BCW (Michie et al., 2011), COM-B model, and PRIME Theory (West & Michie, 2020), and incorporates the following mechanisms:

- **Education:** Informative content on impulsivity and inhibitory control enhances understanding and behavioural capability. Educational approaches have been shown to reduce impulsivity (Santos et al., 2025).
- **Alternative Behaviours:** Participants are encouraged to practise behavioural activation strategies (e.g. attention shifting, seeking support), which reduce maladaptive behaviours like PUI (Park et al., 2016).
- **Persuasion:** Personalised feedback and emotionally engaging messages promote motivation and behavioural reflection (Heijde et al., 2015; Yan et al., 2020).
- **Self-monitoring and Reframing:** Feedback based on self-monitoring supports cognitive restructuring and has been effective in improving self-regulation and reducing internet addiction (Dietvorst et al., 2024; Du et al., 2010; Park, S et al., 2016).
- **Enablement:** Confidence-building tasks (e.g. 3-day impulsivity challenge) help reduce psychological barriers and support change (David et al., 2024).
- **Gamification:** Therapeutic games reinforce inhibitory control strategies and have shown positive effects on PUI and impulsivity (Ayub et al., 2023; Zhan et al., 2024).

The intervention also draws on evidence supporting the use of cognitive behaviour therapy (CBT), motivational interviewing, and cognitive bias modification to reduce impulsivity (Aguilar-Yamuza et al., 2024; Kowalik & Delfabbro, 2025). Participants at high risk receive in-depth modules on impulsivity and its link to PUI, while those at lower risk receive general guidance on inhibitory control and internet use.

For a detailed week-by-week breakdown and more information on each component of the intervention in relation to behaviour change see Appendix B.

Control Condition

Participants in the control condition will receive a structured, digital, non-interactive educational programme. This content will be time-matched to the active interventions, to control for non-specific therapeutic effects associated with time spent engaging in the study. This approach also helps to minimise researcher allegiance bias, which can occur when using waitlist or "treatment as usual" controls.

- The educational material will cover general topics related to:
- Internet use and digital habits
- Emotional well-being
- Dysfunctional behavioural patterns
- Suggestions for alternative, healthier activities

Importantly, this control condition is informational only, with no interactive or skill-building components. This design is grounded in evidence suggesting that while providing information is a necessary foundation, it is not sufficient to produce meaningful behavioural change on its own (Humphreys et al., 2021). Research consistently shows that effective digital health interventions require interactive, motivational, and skill-based elements to facilitate actual behaviour change (Hou et al., 2014).

Thus, the control condition serves as a credible comparator that accounts for participant engagement and time investment, without introducing the active ingredients known to drive behavioural outcomes.

For a week-by-week transcript of the information given to the control participants please see Appendix C.

3.3. Study Design

Pilot Study

The Pilot Study is a controlled, individually randomised, observer-blinded, parallel group, three-arm trial. Participants will be allocated to:

Emotional (Affect) Regulation intervention: Strategies for improving affect regulation (affective responses to triggers, worrying), and increase in social skills see section 3.2 and appendix A.

Inhibitory (Executive) control intervention: Strategies for improving executive (inhibitory) control (boundary setting for internet usage, alternative activities, dealing with urges, habits and cognitive bias modification) see section 3.2 and appendix B.

Control: Manualised digital non-interactive information-provision (education) matched with A and B for time investment see section 3.2 and appendix C.

Each intervention will last for four weeks and will be preceded by a two-week baseline assessment period (see tables 1&2), with a post intervention outcome assessment conducted directly at the end of the four weeks intervention (primary end point), and a follow-up for outcome assessment conducted 3-months later (final end point). Figure 1 shows the flow chart detailing study processes, highlighting the stages leading from participant recruitment to final data analysis. At the end of each assessment and intervention time point participants will be asked to provide feedback about their experience of using the app and elements to evaluate the feasibility and acceptability of the app.

Outcomes: The full list of outcome measure assessments including the period of mobile sensing is shown in table 1 and further details about each assessment and mobile sensing variable can be found in section 6.1.1. The primary main outcome measure assessment for both the pilot study and the RCT will be PUI severity as measured using the PIUQ-SF-9 (Demetrovics et al., 2008). Outcomes will be assessed digitally via a series of self-report questionnaires after sending out push-notifications for invitation as well as reminders in case of non-completion. Additional outcome data is collected via the Dragon Game app, which includes cognitive assessment tasks for affect regulation and inhibitory executive control. As a complementary modality for secondary outcome assessment, smartphone behaviour (data tracking) will also be measured.

The research team are currently seeking funding to include an optional extension to Cohort 2. The optional cohort 2 extension will directly follow on immediately from the original 3-month assessment time point and will last a maximum of 28 months to extend data collection until the end of July 2028. Participants who consent to taking part in the extension phase of Cohort 2 will be followed up during this period, receiving push-notifications to complete assessments derived from the same panel as the original phase, every 3 months until the 31-month final endpoint. Additional data will be collected via the Dragon Game app, which includes the cognitive assessment tasks for affect regulation and inhibitory executive control. Should the research team be successful in obtaining funding, a push-notification will appear asking those who consented to take part in the extension to re-confirm their agreement will appear. Should the research team not be successful, a push-notification will appear thanking them for their consent and time but notifying them that this will be the end of their study involvement (see table 3 for an overview of the extension assessments).

Table 1. Schedule of Assessments outcome measures for both interventions and control.

Assessment/Intervention	Baseline T0 (week 0 to week 2)	Intervention (week 2 to week 6)	Post Intervention T1 (week 6)	Monthly ratings (cohort 2 & 3, week 10 & 14) (cohort 3 only, week 18, 22 & 26)	Follow-up Up T2 (Pilot cohort 2: week 18, RCT; week 30,)
Demographics					
Sex	X				
Gender	X				
Age	X				
Year group at school	X				
Mental Health diagnosis	X				
PUI and clinical variables					
S-CIUS*	X		X	X	X
PIUQ	X		X		X
ISAAQ-10 Part B	X		X		X
ISAAQ-ED	X		X		X
ACSID-5	X		X		X
DASS-21	X		X		X
PaedS	X		X		X
SOCS	X		X		X
SDQ	X		X		X
Browser activity	X		X		X
Inhibitory control					
BrainPac SST	X				X
CHI-T	X		X		X
Question on patience	X				X
Emotional regulation					
BrainPac VMAC	X				X
ERQ-CA	X		X		X
Question on mood	X				X
Persons' characteristics					
UPPS-P	X		X		X
Vaccine hesitancy	X				X
Misinformation	X				X
Physical health					
Height and weight	X				X

Favourite Sports interests	X			X
Internet use expectancies, Internet use experiences, FoMO				
IUES	X		X	X
EGS/ECS	X		X	X
SRHI	X		X	X
FoMO	X		X	X
School performance, family background,				
School marks	X			X
Family background	X			X
Socioeconomic status (FAS)				
Mobile sensing⁺				→
Assessment of cost and burden of PUI				
PQ-LES-Q	X			X
EQ-5D-Y	X			X
Alcohol consumption	X			X
WHODAS 2.0	X		X	X
Ambulatory assessment (AmbA)[#]				
AmbA			X	X

*Note. # Assessed for 7 continuous days. + Continuous recording, -> denotes the period of continuous recording *Collected monthly between T1 and T2, A number of these assessments will also be used during the Intervention (see table 2)*

S-CIUS: Short-Compulsive Internet Use Scale

PIUQ: Problematic Internet Use Questionnaire

ISAAQ-10 Part B: Internet Severity and Activities Addiction Questionnaire - Focus on activities

ISAAQ-ED Internet Severity and Activities Addiction Questionnaire – Eating Disorder

ACSID-5: Assessment of Criteria for Specific Internet-use Disorders

DASS-21: Depression Anxiety Stress Scale

Paeds: Paediatric Self-Stigmatization Scale

BrainPac Stop-Signal-Task (SST)

SOCS: Short Obsessive Compulsive Disorder Screener

SDQ: Strengths and Difficulties Questionnaire

BrainPac- enhanced Value-Modulated Attentional Capture

ERQ-CA: Emotion Regulation Questionnaire for Children and Adolescents

UPPS-P: Urgency – Premeditation - Perseverance - Sensation Seeking - Positive Urgency

CHI-T: Cambridge-Chicago Compulsivity Trait Scale

IUES: Internet Use Expectancies Scale

EGS/ECS: Experience of Gratification Scale and Experience of Compensation Scale

SRHI: Self-Report Habit Index

FoMO: Fear of Missing Out Scale

FAS: Family affluence scale III

PQ-LES-Q: Pediatric Quality of Life Enjoyment and Satisfaction Questionnaire

EQ-5D-Y: European Quality of Life 5 Dimensions

WHODAS 2.0: World Health Organisation Disability Assessment Schedule (adapted for internet use)

Table 2. Schedule of Intervention Assessments and Tasks intrinsic to, for both interventions with high and low PUI.

Assessment/Intervention	Intervention I (4 weeks, weeks 3-6)			
	W3	W4	W5	W6
Both Interventions				
PUI and clinical variables				
S-CIUS		X		
PRISM Internet				
Browser activity	X		X	
Mood-Barometer	X		X	
Self-developed PRISM Internet	X>			
Persons' characteristics				
RR & SER	X			
DBQ-I	X			
Need to belong	X			
UCLA Loneliness Scale	X			
Sofalizing scale	X>			
Internet use expectancies, Internet use experiences, FoMO				
IUES	X>			
FoMO	X>			
FoMO single	X			
Mobile sensing⁺ including App Sessions and Aggregated App usage				
Ambulatory assessment (AmbA)[#]				
AmbA		X>		
Emotional Regulation intervention				
Emotion Memory game		X		
ERQ-CA		X		
Components and functions of emotions video		X		
Pictures with functions of emotions		X		
Emotions and Internet use			X>	
Emotion regulation strategies			X	
Transfer of strategies			X	
Connecting emotion with thoughts (psychoeducation)				X
Connecting Emotion with thoughts (memory game)				X

Transfer to daily life	X>
Emergency plan	X
Inhibitory control intervention	
UUPS-P	X>
CHI-T	X
Impulsive Behaviour/consequences video	X
Challenge to observe behaviour	X
Skills for impulse control	X
Psychoeducation (text) connecting impulsivity with PUI	X>
Specific alternative behaviours for PUI	X>
Dealing with problems	X>
Transfer of strategies	X>
Emergency plan	X>

Additional Intervention tasks both intervention A and B

- Breath analyser
- Positive self-instructions

Note. # Assessed for 7 continuous days, -> denotes the period of continuous recording. + Continuous recording, > High PUI risk group only.

S-CIUS: Short-Compulsive Internet Use Scale

PRISM Internet, self-developed importance activity

RR & SER: Readiness and Self-efficacy Ruler

DBQ-I: Decision Balance Questionnaire

ERQ-CA: Emotion Regulation Questionnaire for Children and Adolescents

UPPS-P: Urgency – Premeditation - Perseverance - Sensation Seeking - Positive Urgency

CHI-T: Cambridge-Chicago Compulsivity Trait Scale

IUES: Internet Use Expectancies Scale

FoMO: Fear of Missing Out Scale

FoMO single: Fear of Missing Out single question

[figure not shown]

Figure 1. Flow diagram of Pilot study. For the control group, the division into high and low PUI risk will be for analysis purposes only. The two theory driven interventions (emotional regulation; inhibitory control) are delivered as high and low intensity versions, based on assessment of PUI risk at baseline. However, both low and high intensity forms of intervention are analysed collectively within each theoretical interventional model.

Table 3: Schedule of assessments for the optional extension to the pilot cohort (cohort 2). At week 18 of the pilot study, participants receive a push notification to re-confirm agreement to take part in the study extension. Assessments then take place at the indicated time-points.

Variable	Assessment time-point (months after entry to the extension period)																										
	1	2	3	4	5	6	7	8	9	10	11	12	13	14	15	16	17	18	19	20	21	22	23	24	25	26	27
PUI and clinical variables																											
S-CIUS	x	x	x	x	x	x	x	x	x	x	x	x	x	x	x	x	x	x	x	x	x	x	x	x	x	x	
PIUQ						x				x					x			x				x					
ISAAQ-10 Part A						x				x					x			x				x					
ISAAQ-10 Part B						x				x					x			x				x					
ISAAQ- ED						x				x					x			x				x					
ACSID-5						x				x					x			x				x					
DASS-21						x				x					x			x				x					
Alcohol items						x				x					x			x				x					
PaedS						x				x					x			x				x					
Vaccine Hesitancy						x				x					x			x				x					
Misinformation						x				x					x			x				x					
Browser activity						x				x					x			x				x					
Inhibitory control																											
BrainPac SST																											
Emotional regulation																											
BrainPac VMAC																											
Physical health																											
Height and Weight	x						x				x				x			x			x			x			
Internet use expectancies, experiences and fear of missing out																											
IUES	x						x				x				x			x			x			x			
EGS/ECS	x						x				x				x			x			x			x			
FoMO	x						x				x				x			x			x			x			
Mobile sensing +																											
Assessment of cost and burden of PUI																											
PQ-LES-Q		x					x				x				x			x			x			x			
EQ-5D-Y		x					x				x				x			x			x			x			

Note: + Continuous recording, -> denotes the period of continuous recording. % Optional assessment, with additional incentive offered for completion (in countries using incentives, incentive to be determined by individual sites).

PUI: *Problematic Use of the Internet*;

S-CUIS: *Short-Compulsive Internet Use Scale*;

PIUQ: *Problematic Internet Use Questionnaire*;

ISAAQ-10 PartA: *Internet Severity and Activities Addiction Questionnaire – Focus on symptom severity*;

ISAAQ-10 Part B: *Internet Severity and Activities Addiction: Questionnaire – Focus on activities*; ISAAQ-ED: *Internet Severity and Activities Addiction Questionnaire- Eating Disorder*;

ACSID-5: *Assessment of Criteria for Specific Internet-use Disorders*;

DASS: *Depression Anxiety Stress Scale*;

PaedS: *Paediatric Self-Stigmatization Scale*;

BrainPac SST: *BrainPac Stop-Signal-Task*

BrainPac VMAC: *BrainPac- enhanced Value-Modulated Attentional Capture*

IUES: *Internet Use Expectancies Scale*;

EGS/ECS: *Experience of Gratification Scale and Experience of Compensation Scale*; FoMO: *Fear Of Missing Out Scale*;

PQ-LES-Q: *Pediatric Quality of Life Enjoyment and Satisfaction Questionnaire*;

EQ-5D-Y: *European Quality of Life 5 Dimensions*.

[figure not shown]

Figure 2. Flow diagram of the optional extension phase. Participant will initially consent to the extension phase during the consent process of the Pilot study. At the 3-month follow-up participants who consented to take part in the extension phase will be sent a push notification through the app to confirm their assent to continue. The 3-month follow-up assessments will be used as a baseline measure for the extension phase.

Randomised Control Trial

The RCT is a controlled, individually randomised, observer-blind, parallel-group, three-arm trial. Participants will be allocated to:

Tailored Arm: Tailored allocation to the Emotional regulation intervention or the Inhibitory control intervention based on prediction of outcome algorithms developed in the Pilot Study.

Random Arm: Random allocation to the Emotional regulation intervention or Inhibitory control intervention.

Control Arm: non-interactive information-provision (education) on safe and effective use of the internet.

Each intervention will last for four weeks, preceded by a two-week baseline assessment (see tables 1&2) period, with a post intervention outcome assessment conducted directly at the end of the four weeks intervention (primary end point), and a follow-up for outcome assessment conducted 6-months later (final end point). Outcomes will be assessed digitally via a series of self-report questionnaires after sending out push-notifications for invitation as well as reminders in case of non-completion. Additional outcome data is collected via the Dragon Game app, which includes cognitive assessment tasks for affect regulation and inhibitory executive control. As a complementary modality for outcome assessment, smartphone behaviour (data tracking) will also be measured. Figure 3 shows the flow chart detailing study processes, highlighting the stages leading from participant recruitment to final data analysis.

Outcomes: The full list of outcome measure assessments including the period of mobile sensing is shown in table 1 and further details about each assessment and mobile sensing variable can be found in section 6.1.1. The primary main outcome measure assessment for both the pilot study and the RCT will be PUI severity as measured using the Problematic Internet Use Questionnaire in its short version (PIUQ-SF-9)(Demetrovics et al., 2008) Outcomes will be assessed digitally via a series of self-report questionnaires after sending out push-notifications for invitation as well as reminders in case of non-completion. Additional outcome data is collected via the Dragon Game app, which includes cognitive assessment tasks for affect regulation and inhibitory executive control. As a complementary modality for secondary outcome assessment, smartphone behaviour (data tracking) will also be measured

[figure not shown]

Figure 3. Flow diagram of RCT study. Allocation takes place twice; at week 0 all participants are randomised to either the tailored allocation arm or the random allocation arm or the control arm. At week 2 participants in the tailored allocation arm are allocated to the emotional regulation intervention or the inhibitory control intervention based on prediction of outcome algorithms developed in the Pilot Study. In the random allocation arm participants are randomised to either the emotional regulation arm or the inhibitory control arm. Regardless of the theoretical model of intervention (emotional regulation; Inhibitory control) all participants in either the tailored allocation arm or the randomised allocation arm will be analysed together as we are interested in the effect of the method of allocation on outcomes.

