Students can choose their preferred language on the BootstrApp. A holding page will then appear, stopping them from proceeding until consent and assent has been verified by a research team member.

Student Session

Students within the designated age range will be invited to attend an information session hosted by the research team and, possibly, their school ambassadors.

The research team will verify that both the parent or guardian's Informed Consent Form (ICF) and the student's assent has been provided. Once both have been confirmed, a unique code will be assigned to the form(s), and the student will be asked to enter this code into the BootstrApp. Once this code is entered, the student is officially enrolled and will begin the two-week assessment phase. The unique codes will be automatically generated before recruitment begins by the app development team and will consist of 8 alphanumeric characters.

Depending on local circumstances, the above activities may not all take place during a single information session but may be arranged separately.

The unique code ensures that the student's assent can be linked to their parent's authorisation if needed, such as in cases of premature withdrawal, and confirms that parental or guardian consent has been obtained. This code also identifies the time zone to send push notifications at the correct times and the school. For students whose parents have opted out, it will be clearly communicated that they will not be able to participate.

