4.4. Baseline

Once enrolled in the pilot or RCT, students will begin automated data collection via the BootstrApp Intervention app. The list of baseline (T0) questionnaires is provided in Table 1.

Depending on local school agreements, assessments may be completed during class or at home. To support retention, students can complete the assessments in one sitting or across multiple days. While the target is to complete baseline assessments within 4 days, the window may be extended to 14 days if needed.

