4.5. Randomisation

In both the pilot and RCT studies, randomisation will be carried out using individualised, server-based assignment, based on each participant's access code at registration.

Pilot study: For the pilot study each participant will have an equal probability (33.3%) of being allocated to one of the three groups: Emotional regulation intervention group, Inhibitory control intervention group, or the control group.

RCT: For the RCT, each participant will have an equal probability (33.3%) of being allocated to one of three arms: tailored allocation, random allocation, control. This means that participants will have a 66.6% chance of allocation to an active intervention and 33% chance of allocation to the control arm.

Participants allocated to the random allocation arm will have a 50% chance of receiving the emotional regulation or inhibitory control intervention.

In the tailored allocation arm, participants will receive the intervention (targeting emotional regulation or inhibitory control) predicted as most likely to be effective for them by comparing their baseline profile (against the profile of response-predictors developed during the pilot study).

For both the pilot study and the RCT, both participants and researchers will remain blinded to the group allocation to minimise bias. The statistical analysis will be completed on blinded data (allocation A, B or C), with the blinding only being broken when the primary analysis has been completed.

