6.3.2. Primary analyses

Pilot Study

The pilot study has one primary research question:

- Can routinely collected data at baseline (passive sensory data, or psychometric measures) predict which intervention will be more effective for an individual (based on baseline assessments and machine learning (ML) algorithms).

A secondary research question is

How effective are each of the active interventions at reducing PUI risk compared to the control group.

The pilot study will include three groups, Emotional Regulation intervention, Inhibitory Control intervention and a control group. A fourth validation group for testing the ML algorithm will be drawn as a random sample of 1/3rd of participants from each study arm, resulting in a total sample size of 4 × 838 = 3,352 participants. All other analyses will be secondary and evaluated using General Linear Models (GLM).

Behavioural data from all measures will be aggregated into sum scores or mean scores as appropriate. Efficacy evaluation will be conducted using General Linear Modelling, accounting for demographic and psychological variables. The primary analysis will focus on between-group comparisons, estimating group differences with 95% confidence intervals and calculating effect sizes.

Machine Learning Approach

To predict psychological phenotypes from multisource big data, we will apply a rigorous ML approach underpinned by psychological theory (Montag & Rumpf, 2021). The pilot study data will be used to develop predictive algorithms identifying which individuals are most likely to benefit from the emotional regulation intervention or the inhibitory control intervention.

We will build multivariate predictive models using both classical methods (logistic regression, support vector machines (SVMs), Random Forest, boosted trees (XGBoost)) and advanced techniques (deep neural networks, domain adaptation, deep representations, adversarial training). These models will link assessment data to individual-level outcomes, incorporating risk assessments from the assessment study alongside a range of input dimensions, including:

- Digital behaviour: Repetitive patterns, diurnal variation, app usage types
- Neurological assessments: Reaction time, error ratio
- Personality dimensions: Compliance rate, communication patterns

Learning Representations

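### The RCT randomises to arm at week 0, before the baseline data that tailoring needs; randomising at week 2 after a minimum baseline set would avoid dilution and early loss at small cost

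*Protocol*

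**What the plan says.** The Figure 3 legend in Protocol 3.3 describes two allocations in the RCT. The first is to arm: "at week 0 all participants are randomised to either the tailored allocation arm or the random allocation arm or the control arm". The second is to intervention: "At week 2 participants in the tailored allocation arm are allocated to the emotional regulation intervention or the inhibitory control intervention", while random-arm participants are randomised between the same two interventions.

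Protocol 4.5 places the server-based assignment at enrolment, "based on each participant's access code at registration". Protocol 4.3 shows that this precedes baseline: "Once this code is entered, the student is officially enrolled and will begin the two-week assessment phase". Protocol 4.4 sets a target of 4 days for baseline, but "the window may be extended to 14 days if needed".

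The tailored choice is made "by comparing their baseline profile" with the response predictors found in the pilot (4.5). Section 6.3.2 describes the candidate baseline predictors as "passive sensory data, or psychometric measures". The high-risk version of either active intervention depends on a baseline S-CIUS score of 9 or more (4.6).

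The Figure 3 legend also says that everyone in an allocation arm is analysed together, whichever intervention they received. Section 6.3.2 lists tailored versus random allocation as one of three primary questions. Nowhere does the protocol require baseline to be complete before allocation, or say what a tailored-arm participant without a usable profile receives. The multiple-imputation text in 6.3.1 and 6.3.3 concerns analysis, not allocation.

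**The concern.** The arm is fixed two weeks before anything uses it and before the data that one arm depends on exist. A random-arm participant needs no profile to be given one of the two interventions. A tailored-arm participant does. If the inputs are missing at week 2, the app has nothing to tailor on, and the participant can only receive an untailored choice while still counting as tailored.

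Two things are at stake. The tailored-versus-random difference, which is the purpose of the RCT, shrinks in proportion to the untailored share of the analysed tailored arm. And everyone who leaves during the two baseline weeks is a randomised loss in all three arms, although no arm-specific content has yet been delivered. Neither is necessary, because a second allocation step already runs at week 2.

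**Working it through.** **Inputs from the protocol (3.4.2).** Alpha 0.05, power 0.80, effect size d = 0.3, 176 per group, 70% completion, 30% at risk, 838 per group, 2,514 in total. The Study Summary plans 3,600 per cohort.

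**Reproducing the plan's figure.** A two-sided two-sample t-test with d = 0.3 needs 175.4 per group, rounded up to 176 (a one-sided test would need only 138). Then 176 / 0.3 / 0.7 = 838.1, and 3 × 838 = 2,514. The stated sample size reproduces, and the timing of randomisation does not alter it.

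**Order of events.**

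| Time | Event | Uses the arm? |
|---|---|---|
| Week 0 | Code entered, enrolment, arm randomised | Assigned only |
| Weeks 0 to 2 | Same baseline for all arms | No |
| Week 2 | Intervention allocated; tailored arm by baseline profile | First use |
| Weeks 2 to 6 | Intervention | Yes |
| Week 6 | Primary endpoint | Yes |

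**Dilution.** Let f be the share of the analysed tailored arm that could not be tailored and received a random choice instead. On average these participants do not differ from the random arm, so the observed difference is 0.30 × (1 − f). By the normal approximation, power at n per group is Φ(d × √(n/2) − 1.96), with √(176/2) = 9.381.

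| f (assumed) | Diluted d | Power at 176 per group |
|---|---|---|
| 0 | 0.300 | 80.4% |
| 2.9% | 0.291 | 78.1% |
| 5.7% | 0.283 | 75.6% |
| 10% | 0.270 | 71.7% |
| 20% | 0.240 | 61.5% |

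The protocol gives no value for f. The rows for 2.9% and 5.7% show one way in which f stays small. Suppose 10% or 20% of registrants do not complete baseline, one in five of these still supplies the week 6 outcome, and overall completion is 70%. Then f = 0.20 × 0.10 / 0.70 = 2.9%, or 0.20 × 0.20 / 0.70 = 5.7%. The last two rows apply only if f itself is 10% or 20%.

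**Enrolment if randomisation moves to week 2.** Let b be the assumed share of registrants who do not complete baseline. If the 70% is counted from randomisation at week 2, registrations must be 2,514 / (1 − b):

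- b = 10%: 2,514 / 0.90 = about 2,793
- b = 20%: 2,514 / 0.80 = about 3,142
- b = 30%: 2,514 / 0.70 = about 3,591

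All are within 3,600. If the 70% already covers baseline loss and is counted from enrolment, registrations stay at 2,514.

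**The case against.** A reader might infer that every baseline non-completer in the tailored arm dilutes the contrast, so that 10% to 20% non-completion would cost 8 to 19 points of power. The documents do not support that.

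- The 176 are high-risk children with follow-up. High risk is defined by the baseline S-CIUS, so anyone without that score cannot be among the 176 in any arm. Only those with an S-CIUS but without other required inputs can dilute that group.
- Many who skip baseline will also lack the outcome at week 6. They fall within the 30% loss already allowed for and add missing data, not dilution.
- Passive sensing is a candidate predictor, so some questionnaire non-completers might still be tailored. The algorithm's required inputs will be known only after the pilot.

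A reader might also infer selective loss from the tailored arm and hence bias. No section drops baseline non-completers from one arm only. The arms share the same baseline, and participants and researchers are blinded (4.5), so drop-out before week 2 should not differ by arm. Nor is the gap confined to the tailored arm, since the high- and low-risk versions of both active interventions also need the baseline S-CIUS.

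Finally, later randomisation is not free. It narrows a trial intended for the whole adolescent population (3.1.1) to those who complete baseline. A stated fallback, with all randomised participants analysed in their arm, would close the gap in the rules while keeping week 0.

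These points limit the size and rule out a claim of demonstrated bias. They do not give a reason for fixing the arm at week 0. A fallback rule would settle what untailored participants receive, but would leave both the dilution and the early randomised loss in place.

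**Conclusion.** The point holds as a cheap improvement to the RCT design. The arm is randomised before any baseline data exist, has no effect until week 2, and in one arm depends on those data. The consequences are dilution of a primary contrast and avoidable post-randomisation loss.

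The size cannot be determined from the protocol. It is a few points of power if the untailored share of the analysed tailored arm is around 3% to 6% (80% to about 78% to 76%). It becomes substantial only if that share reaches 10% to 20% (about 72% to 61%). These figures assume a true tailored-versus-random difference of d = 0.3, independent observations at the plan's 176 per group, and a random choice of intervention for those who cannot be tailored.

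**What to change.** In the RCT, trigger the three-arm randomisation at week 2 on completion of a defined minimum baseline set: PIUQ, S-CIUS and the inputs that the final algorithm requires. Do this in the same server step that now assigns the intervention. State what counts as sufficient data, so that partial completers are handled by rule, and count the 70% completion from that point. Amend the Figure 3 legend and sections 3.4.2 and 4.5 to match.

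The cost is server configuration and protocol wording before the RCT starts. The randomised population becomes baseline completers, and this should be stated when the results are generalised. Registrations must exceed 2,514: about 2,793 to 3,142 at an assumed 10% to 20% baseline non-completion, within the planned 3,600.

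If week 0 is kept, the minimum is to state the fallback allocation for participants without usable inputs and to confirm that all randomised participants are analysed in their arm. Stratifying the randomisation and changing the timing in the pilot, which has no tailored arm, are separate preferences and are not needed here.
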